## **EFFICACY ANALYSES**

Overall response rate as defined by achieving:

- In solid tumours, confirmed complete response (CR) and/or partial response (PR) will be presented by percentage rates and 95% confidence intervals (CI). For changes in solid tumour size, waterfall plots will be presented.
- In T-ALL/T-LBL patients, confirmed Complete Remission (CR) and/or Complete Remission with Incomplete Hematologic Recovery (CRI) will be presented by percentage rates and 95% CI.
- For solid tumour indications: clinical benefit rate at Month 3, 6, and 9, as defined by achieving complete response (CR) and/or partial response (PR) and/or stable disease (SD) will be assessed by RECIST 1.1 and presented by percentage rates and 95% CI. Waterfall plots will be presented.
- For T-ALL/T-LBL patients: the ORR is the sum of patients achieving a CR or a CRI divided by the total number of patients with T-ALL/T-LBL treated. Assessment of efficacy will be performed on results of bone marrow biopsies or aspirates, blood and CSF samples, and PET-CT in patients with extramedullary disease, based on the NCCN Guidelines on Adult Acute Lymphoblastic Leukemia (Version 1.2020).

For all response assessments, swimmers plots will be presented. All response assessments will be listed.

The duration of response defined as time from first assessment of PR or CR in solid tumours or CRI in T-ALL/T-LBL to follow-on first assessment of PD or relapse will be summarised by descriptive statistics including median duration of response and respective 95% CI. Duration of response will also be listed.

Time from first treatment received until progressive disease (PD)/OS will be summarised by Kaplan-Meier estimates, median PFS/OS and respective 95% confidence intervals. Patients with no event will be censored at the last available tumour assessment for PFS and at the last timepoint known alive for OS.

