## **10.6.2 Efficacy Analyses**

### **Overall response rate:**

For solid tumours, overall response rate as defined by achieving confirmed complete response (CR) and/or partial response (PR) will be presented by percentage rates and 95% confidence intervals. For changes in solid tumour size waterfall plots will be

presented. For all response assessments, swimmers plots will be presented. All response assessments will be listed.

In T-ALL/T-LBL, overall response rate defined as achieving confirmed Complete Remission (CR) and/or Complete Remission with Incomplete Hematologic Recovery (CRi) will be presented by percentage rates and 95% confidence intervals (CI).

**Clinical benefit rate for solid tumours at Month 3, 6, and 9, and for T-ALL/T-LBL at 1, 2, and 3 months, and every 2 months from Month 3 to Month 9:**

Clinical benefit rate as defined by achieving complete response and/or partial response and/or stable disease (SD) will be presented by percentage rates and 95% confidence intervals. Waterfall plots will be presented.

- For solid tumour indications: Clinical benefit rate (CR + PR + SD), assessed by RECIST 1.1.

**Duration of response:** The duration of response defined as time from first assessment of PR or CR in solid tumours or CR/CRi in T-ALL/T-LBL to follow-on first assessment of PD or relapse will be summarised by descriptive statistics including median duration of response and respective 95% CIs. Duration of response will also be listed.

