## **Appendix 8 Response Assessment in Acute Lymphoblastic Leukaemia/ Lymphoblastic Lymphoma**

### **Response criteria for Blood and Bone Marrow:**

- CR
  - No circulating lymphoblasts or extramedullary disease
  - No lymphadenopathy, splenomegaly, skin/gum infiltration/testicular mass/CNS involvement
  - Trilineage haematopoiesis (TLH) and <5% blasts
  - Absolute neutrophil count (ANC) >1000/microL
  - Platelets >100,000/microL
  - No recurrence for 4 weeks
- CR with incomplete blood count recovery (CRi)
  - Meets all criteria for CR except platelet count or ANC
- Overall response rate (ORR = CR + CRi)
- **NOTE:** MRD assessment is not included in morphologic assessment and should be obtained
- Refractory disease
  - Failure to achieve CR at the end of induction
- Progressive disease (PD)
  - Increase of at least 25% in the absolute number of circulating or bone marrow blasts or development of extramedullary disease
- Relapsed disease
  - Reappearance of blasts in the blood or bone marrow (>5%) or in any extramedullary site after a CR

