### 5.6.2.2 Overall Response Rate (ORR)

Overall response rate (ORR), i.e. rate of patients with response (CR+PR for RECIST V1.1), will be presented together with corresponding Clopper-Pearson 95% CI for each dose group with at least 6 patients. For changes in solid tumour size, waterfall plots will be presented. For all response assessments, swimmers plots will be presented. All response assessments will be listed.

For T-ALL/T-LBL patients, the overall bone marrow response rate as per local assessment, the number (n) and percentage (%) of patients with progressive disease [PD], refractory and relapsed disease will be summarized by cycle and overall for each dose group and overall, with 95 % CI. In addition to bone marrow the mediastinal response, CNS and extramedullary responses will be presented in the same way but only for subset of patients with extramedullary involvement at baseline. Swimmers plots will be generated for graphical display of response. Clopper-Pearson (exact) method will be used to derive the CI.

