### 5.6.2.3 Time to response (TTR) and Duration of response (DOR)

TTR is defined as the time from the first day of study treatment to the first date the response criteria are met, given they were later confirmed. Patients who are not confirmed responders will be censored at the time of their last evaluable tumour assessment. Patients with no tumour assessment after the baseline visit will be censored at the time of the first day of study treatment plus 1 day.

For each dose group, estimates of the median TTR and the corresponding two-sided 95% CI will be presented along with the estimates for the 25th and 75th percentiles and the associated ranges (minimum, maximum) using the Kaplan-Meier (KM) approach.

DOR is defined only for the patients with a confirmed response according to RECIST, v1.1 for patients with solid tumours, according to NCCN guidelines for patients with haematologic malignancies.

By definition, DOR is the time interval between the date of the earliest qualifying response and the date of PD or death from any cause, whichever occurs first. For patients who are alive without progression following the qualifying response, DOR will be censored on the date of last evaluable tumour assessment or last FU for PD before the data cutoff date. Data for patients who are lost to FU prior to documented progression will be censored at the last tumour assessment date which the patient is known to be progression-free prior to the data cutoff date.

For each cohort, estimates of the median DOR and the corresponding two-sided 95% CI will be presented along with the estimates for the 25th and 75th percentiles and the associated ranges (minimum, maximum) using the Kaplan-Meier (KM) approach.

Both TTR and DOR will be provided in Listing.

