#### **5.6.2.5 Progression Free Survival (PFS) and Overall Survival (OS)**

PFS, measured in days, is defined as the time from the first day of study treatment until the first documented progression of disease or death from any cause, whichever occurs first.

PFS for patients who have neither progressed nor died will be censored on the date of last evaluable tumour assessment prior to the data cut-off date. For patients who have not died and have no recorded post-BL tumour assessment, PFS will be censored on the date of the first dose of study medication plus 1 day. Patients who die without any recorded post-baseline tumour assessment after receiving the first dose will be considered to have an event on the date of death. Data for patients who are lost to FU prior to documented progression will be censored at the last evaluable tumour assessments date which the patient is known to be progression-free prior to the data cut-off date.

For each dose group with at least 6 patients, estimates of the median PFS and the corresponding two-sided 95% CI will be presented along with the estimates for the 25th and 75th percentiles and the associated ranges (minimum, maximum) using the Kaplan-Meier (KM) approach.

OS is defined as time between the first day of study treatment and date of death of any cause. Patients for whom no death is captured on the clinical database are censored at the last date they were known to be alive. Patients with no post-BL information will be censored at the time of first study treatment plus 1 day.

For each dose group at least 6 patients, estimates of the median OS and the corresponding two-sided 95% CI will be presented along with the estimates for the 25th and 75th percentiles and the associated ranges (minimum, maximum) using the Kaplan-Meier (KM) approach.

Both PFS and OS details will be provided in Listing.

Futher survival status information from long-term FU will be listed in Listing.

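### The SAP ends duration of response at PD or death and omits relapse, which the protocol counts for T-ALL/T-LBL; PFS has the same gap, inherited from the protocol

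*SAP*

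**What the plan says.** **DOR in the SAP.** Section 5.6.2.3 states that "DOR is the time interval between the date of the earliest qualifying response and the date of PD or death from any cause", whichever is first. It covers confirmed responders by RECIST in solid tumours and "according to NCCN guidelines for patients with haematologic malignancies". The censoring rule reads: "For patients who are alive without progression following the qualifying response, DOR will be censored on the date of last evaluable tumour assessment" or at the last follow-up for PD.

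**DOR in the protocol.** Section 10.6.2 runs DOR from first PR or CR in solid tumours, or from "CR/CRi in T-ALL/T-LBL to follow-on first assessment of PD or relapse". The synopsis uses the same endpoint: "CRI in T-ALL/T-LBL to follow-on first assessment of PD or relapse". Neither names death.

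**PFS.** SAP 5.6.2.5 measures from first treatment "until the first documented progression of disease or death from any cause, whichever occurs first". The protocol (synopsis and 10.6.2) also names progression and not relapse.

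**What relapse is.** Protocol Appendix 8 gives relapsed disease its own entry, next to but distinct from PD: "Reappearance of blasts in the blood or bone marrow (>5%) or in any extramedullary site after a CR". It defines relapse again for CNS disease and for mediastinal disease. SAP 5.6.2.2 keeps the categories apart: the number and percentage of "patients with progressive disease [PD], refractory and relapsed disease will be summarized by cycle".

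**Declared changes.** SAP section 6 reports no change from the analysis planned in the protocol. SAP section 1 names protocol version 4.1 (3 August 2020) as its source. The protocol in hand is version 4.3 (28 May 2021), and SAP version 2.0 is dated 29 April 2022.

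**The concern.** In T-ALL/T-LBL a remission can end by relapse, and the protocol treats it so: it stops the DOR clock there, and section 5.1.1.1 allows further courses for patients in CR until relapse. An event definition without relapse leaves such a patient, if alive, formally without progression. The patient is then censored because the treatment failed, which is informative censoring, or carried forward to death, which makes DOR partly a measure of survival after relapse. The stake is the remission duration and PFS reported for the one named haematological indication in the Part A confirmatory cohort.

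**Working it through.** The documents give no planned median, event count or sample size for DOR or PFS, so there is no plan figure to reproduce. The check compares definitions and then follows one patient through them.

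**1. End events side by side**

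| Endpoint | Protocol | SAP |
|---|---|---|
| DOR, T-ALL/T-LBL | PD or relapse | PD or death |
| PFS | Progression | Progression or death |
| BOR window | Not compared | Progression or recurrence, death, or end of study (5.6.2.1) |

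For DOR the SAP lacks relapse and adds death. For PFS both documents lack relapse. The SAP is also uneven internally, because its BOR window closes at recurrence and its DOR does not.

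**2. Does PD absorb relapse by definition?** Partly. Appendix 8 defines PD as a rise of at least 25% in the absolute number of circulating or marrow blasts, or new extramedullary disease.
- Marrow: relapse needs blasts above 5%. A value of 5% is a 25% rise from 5 / 1.25 = 4.0%. At equal cellularity, a relapse from a remission level of 4.0% or less also meets PD. From a level between 4.0% and 5%, a relapse just above 5% does not.
- Blood: CR requires no circulating blasts, so reappearance is a rise from none. That is an increase, although a percentage of zero is undefined.
- Extramedullary: a new site can be read as PD. CNS disease has a relapse definition but no PD definition of its own.

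Many relapses could therefore be coded as PD, but no sentence says that they must be.

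**3. One patient, assumed dates.** CR on day 29 (the scheduled marrow assessment), confirmed later; relapse on day 113; death on day 197. Only day 29 comes from the documents. The SAP 5.1 rule is duration = end - start + 1.
- Relapse as an event: DOR = 113 - 29 + 1 = 85 days.
- SAP wording, death observed: DOR = 197 - 29 + 1 = 169 days, and 169 / 85 = 2.0.
- SAP wording, alive at cut-off: 85 days, censored, if the assessment showing relapse is the last evaluable one.
- PFS from day 1: 113 days with relapse as an event, 197 days without.

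At the extreme, if k responders all relapse and are alive at cut-off, the literal rule counts 0 of k DOR events and the median is not reached. Counting relapse gives k of k.

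**4. Direction and possible size.** A simulation with exponential times and 200,000 draws shows the mechanism. All medians are assumed. Median time from relapse to death is 2, 4 or 6 months, and no relapse is coded as PD.

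| Assumed median to relapse (months) | Median DOR, relapse counted | Event only at death | Half censored at relapse, half followed to death |
|---|---|---|---|
| 2 | 2.0 | 4.8 to 9.1 | 6.2 to 10.5 |
| 3 | 3.0 | 6.0 to 10.7 | 8.1 to 12.7 |
| 6 | 6.0 | 9.2 to 14.5 | 13.7 to 18.7 |

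If every relapse were coded as PD, the second column would apply and there would be no bias.

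**The case against.** The best defence is that PD was meant to include relapse. After confirmed CR or CRi, the marrow schedule (SAP Appendix 3, note 24, and the matching protocol note) continues to PD or end of study, as if PD marked the end of remission. BOR closes at progression or recurrence. As shown above, many relapses also satisfy the PD wording. The list in SAP 5.6.2.2 sets table categories and is not a time-to-event rule. This stands as evidence of intent, and it rules out saying that relapse is excluded by design or can never be an event. It does not supply the missing mapping, so the result depends on an unwritten programming choice.

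Three stronger readings are tempting, and the documents do not support them.
- A reader might infer that the SAP removed relapse from PFS. The protocol's PFS never named it, so the conflict between the documents is confined to DOR.
- A reader might infer that the section 6 statement of no changes is false. The SAP cites protocol version 4.1, whose text is not available here, so this cannot be checked. What can be said is that the SAP postdates version 4.3 and does not match it on DOR.
- A reader might take a two-fold lengthening, or any row of the table, as an estimate. These are invented inputs.

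On weight, the objection is largely right. DOR and PFS are secondary and descriptive, the SAP plans no formal hypothesis testing, and Part A's primary endpoints are DLTs and safety. Medians are reported by cohort or dose group, with none specified for T-ALL/T-LBL alone, so other tumour types would dilute the effect. T-ALL/T-LBL is one of several indications sharing about 45 confirmatory patients, and DOR uses confirmed responders only. Relapse also stays visible in the by-cycle tables and the listings.

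**Conclusion.** The point holds for DOR as a conflict between SAP 5.6.2.3 and the protocol, and for PFS as an omission common to both documents. With death kept as an event, leaving out relapse can only lengthen DOR and PFS. Relative to the protocol's DOR the net difference is not one-sided, because the SAP also adds death. The size cannot be derived from the documents. It depends on how many responders relapse, how many of those relapses are coded as PD, and how long patients survive and are followed afterwards; it is zero if all are coded as PD. It does not follow that remission duration will in fact be overstated, only that the written rule permits it. Severity is moderate: the event rule conflicts with the protocol and should be corrected, but it affects descriptive secondary endpoints in T-ALL/T-LBL only.

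**What to change.** - **SAP 5.6.2.3:** for T-ALL/T-LBL, define the DOR event as the earliest of PD, relapse after CR or CRi (blood or marrow, CNS, or extramedullary, per protocol Appendix 8), or death from any cause. Name CRi explicitly, because Appendix 8 words blood and marrow relapse only after a CR.
- **Censoring text in 5.6.2.3:** restrict it to patients alive with neither progression nor relapse. Otherwise the new event definition and the old censoring clause would contradict each other.
- **SAP 5.6.2.5:** apply the same event rule to T-ALL/T-LBL PFS, as a clarification of both documents, and add the matching words to protocol 10.6.2 and the synopsis.
- **SAP section 6:** record whatever still differs from the protocol, including death as a DOR event.

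The cost is a few sentences and one event flag. No new data are needed, since relapse is already to be summarised by cycle. Reported DOR and PFS may be shorter.

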#### **5.6.2.4 Clinical Benefit Rate (CBR)**

Patients with solid tumours are considered to have clinical benefit if they have a tumour assessment status of CR, PR or SD according to RECIST, v1.1.

The CBR at 3 months, 6 months and 9 months after treatment start will be presented together with corresponding Clopper-Pearson 95% CI for each dose group with at least 6 patients.

#### **5.6.2.5 Progression Free Survival (PFS) and Overall Survival (OS)**

PFS, measured in days, is defined as the time from the first day of study treatment until the first documented progression of disease or death from any cause, whichever occurs first.

PFS for patients who have neither progressed nor died will be censored on the date of last evaluable tumour assessment prior to the data cut-off date. For patients who have not died and have no recorded post-BL tumour assessment, PFS will be censored on the date of the first dose of study medication plus 1 day. Patients who die without any recorded post-baseline tumour assessment after receiving the first dose will be considered to have an event on the date of death. Data for patients who are lost to FU prior to documented progression will be censored at the last evaluable tumour assessments date which the patient is known to be progression-free prior to the data cut-off date.

For each dose group with at least 6 patients, estimates of the median PFS and the corresponding two-sided 95% CI will be presented along with the estimates for the 25th and 75th percentiles and the associated ranges (minimum, maximum) using the Kaplan-Meier (KM) approach.

OS is defined as time between the first day of study treatment and date of death of any cause. Patients for whom no death is captured on the clinical database are censored at the last date they were known to be alive. Patients with no post-BL information will be censored at the time of first study treatment plus 1 day.

For each dose group at least 6 patients, estimates of the median OS and the corresponding two-sided 95% CI will be presented along with the estimates for the 25th and 75th percentiles and the associated ranges (minimum, maximum) using the Kaplan-Meier (KM) approach.

Both PFS and OS details will be provided in Listing.

Futher survival status information from long-term FU will be listed in Listing.

## 5.7 Safety

The safety analysis is the primary analysis for this study.

All safety and tolerability assessments will be based on the SS and will be summarized within cohort.

The safety endpoints include the following:

- Incidence of treatment-emergent adverse events (TEAEs), including
  - All adverse events (AE)
  - Serious adverse events (SAEs)
  - Dose-limiting toxicities (DLT)
- Laboratory tests values, including
  - Biochemistry
  - Haematology
  - Urinalysis
  - Cardiac markers
- Vital signs, including
  - Systolic and diastolic arterial blood pressure (BP)
  - Weight and BMI
  - Pulse rate (PR)
  - Oral temperature
- Cardiac function testing, including
  - Electrocardiogram (ECG), including Heart Rate, PR Interval, RR Interval, QRS Interval, QT Interval, QTc Interval
  - Incidence of abnormal ECG findings
  - Left ventricular ejection fraction (LVEF) results
  - Incidence of abnormal echocardiography findings
- Physical examination, including
  - Incidence of abnormal findings

- Incidence of abnormal, clinically significant findings

### 5.7.1 Adverse Events

AEs and SAEs will be summarized by cohort by presenting the number and percentage of patients having any event, number of events is also presented; summaries classifying events according to severity (CTCAE) grade, relationship to study drug, outcome and action taken with study drug will be presented. Missing severity, relationship or outcome will be classed as unknown. If a patient experiences the same AE at more than one severity, or with more than one relationship to investigational product, the most severe rating or the stronger causal relationship to investigational product will be given precedence.

All AEs, related AEs, SAEs, related SAEs, AEs with CTCAE Grade  $\geq 3$ , related AEs with CTCAE Grade  $\geq 3$  as well as AEs leading to premature discontinuation, interruption or discontinuation of study drug or to dose modification will be also summarized presenting the number and percentage of patients having an event in each MedDRA system organ class (SOC) and preferred term (PT) category. A patient with more than one occurrence of the same AE in a particular SOC will be counted only once in the total of those experiencing AEs in that SOC.

All AE, and SAE information collected will be listed as appropriate. A separate summary table and a listing including only DLTs will be also provided.

Only treatment emergent AEs, i.e. AEs occurring on or after day of first administration of study treatment, will be included in the event summaries. Non-treatment emergent events (starting prior to exposure to study treatment) will be included in the patient listings and flagged but not included in the summary tables. Where an AE start date is partially or fully missing, and it is unclear as to whether the AE is treatment emergent, it will be assumed that it is.

All deaths overall will be summarized and listed.

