#### Phase I, Part A – Escalation:

- All patients from each dose cohort in Part A will stay overnight at the hospital for 1 night following their first CB-103 administration (C1D1) to allow for 24-hour PK sampling and ECG monitoring. During this time the patients will be closely monitored for safety. The overnight stays may not be required if reduced ECG and PK sampling is implemented.

In case CB-103 is given BID, one more overnight hospital stays at Day 8 in cycle 1 may be necessary to allow late samples collection.

- Patients will then undergo daily visits for 2 days following the overnight monitoring on Day 1 at the hospital, and will get their CB-103 doses administered in the hospital. Patients will stay at the hospital for at least 3 hours following each administration to allow safety reporting.
- Weekly visits to monitor safety and perform ECG monitoring and PK sampling are planned during the rest of the treatment period for the 1st cycle of CB-103 (28 days).
- Every 2 weeks visits to monitor safety and perform PK sampling are planned from cycle 2 until the completion of cycle 6.
- EOT visit within 14 days after the last dose of CB-103 (within the 6 cycles period).
- Safety follow-up visit (End-of-Study) for each patient within 28 days after the last dose of CB-103.
- Survival follow-up (e.g. per telephone) for 1 year is planned every three months after the End-of-study visit or after the last treatment cycle (if outside of the 6 cycles period).
- Further visits might be considered, depending on the health status of the patient, as determined by the treating Investigator of the respective investigational site.
- More frequent laboratory safety tests (e.g., to closely monitor the liver function), are possible and can be performed outside the study site for those patients leaving far away, if necessary. The laboratory reference ranges from the local laboratories must be collected, and filed in the laboratory report together with the patients' medical records. Care should be taken that any outliers possibly produced by the local laboratory findings are investigated at the study site.

Note: for those patients who may have the option to continue treatment after cycle 6, the subsequent visits are planned every 4 weeks if no medical issue or complication occurred in the previous cycles.

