**Phase I, Part A - MTD/RP2D confirmatory cohort and Phase IIA, Part B – Expansion:**

**For patients with solid tumours who are not hospitalized:**

- Patients will undergo daily visits for 3 days and will get their CB-103 doses administered in the hospital. Patients will stay for at least 3 hours following each administration of CB-103 to allow safety reporting with the exception of the first day where the patients should stay for up to 8 hours post-dose.

In case CB-103 is given BID, one more overnight hospital stays at Day 8 in cycle 1 may be necessary to allow late samples collection.

- Weekly visits to monitor safety and perform ECG monitoring and PK sampling are planned during the rest of the treatment period for the 1st cycle of CB-103 (28 days).
- Every 2 weeks visits to monitor safety and perform PK sampling are planned from cycle 2 until the completion of cycle 6.
- After cycle 6, subsequent visits are planned every 4 weeks if no medical issue or complication occurred in the previous cycles.
- End-of-Treatment (EOT) visit within 14 days after the last dose of CB-103 (within the 12 cycles period).
- Safety follow-up visit (End-of-Study) for each patient within 28 days after the last dose of CB-103.
- Survival follow-up (e.g. per telephone) for 1 year is planned every three months after the End-of-Study or after the last treatment cycle (if outside of the 12 cycles period), and every six months thereafter for the 2nd year.
- Further visits might be considered, depending on the health status of the patient, as determined by the treating Investigator of the respective investigational site.
- More frequent laboratory safety tests (e.g., to closely monitor the liver function), are possible and can be performed outside the study site for those patients living far away, if necessary. The laboratory reference ranges from the local laboratories must be collected and filed in the laboratory report together with the patients' medical records. Care should be taken that any outliers possibly produced by the local laboratory findings are investigated at the study site.

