### **9.3.5.8 Deaths**

Deaths that occur during the protocol-specified Adverse Event reporting period that are attributed by the investigator solely to the progression of the underlying cancer, will be recorded on the EoT/EoS pages in the eCRF and not as an Adverse Event. All other deaths that occur during the protocol-specified adverse event reporting period (see Section 9.3.1), regardless of relationship to study drug, must be recorded on the Adverse Event eCRF and immediately, within 24 hours reported to the Sponsor (see Section 9.4.2).

Death should be considered an outcome and not a distinct event. The event or condition that caused or contributed to the fatal outcome should be recorded on the Adverse Event eCRF. Generally, only one such event should be reported. The term "sudden death" should only be used for the occurrence of an abrupt and unexpected death (i.e., due to presumed cardiac causes in a patient with or without pre-existing heart disease). If the cause of death is unknown and cannot be ascertained at the time of reporting, "unexplained death" should be recorded on the Adverse Event eCRF. If the cause of death later becomes available, "unexplained death" should be replaced by the established cause of death.

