## **10.6.1 Safety Analyses**

### **10.6.1.1 Adverse Events**

The Medical Dictionary for Regulatory Activities (MedDRA) coding dictionary will be applied for the coding of AEs. NCI-CTCAE toxicity Grades will be utilised for classifying severity.

Adverse events, related adverse events, serious adverse events and related serious adverse events, adverse events with NCI CTCAE Grades  $\geq 3$ , related adverse events with NCI CTCAE Grades  $\geq 3$ , adverse events leading to premature discontinuation, interruptions or discontinuation of study drug or dose modification will be analysed descriptively utilising corresponding MedDRA System Organ Classes (SOCs) and Preferred Terms (PTs).

Deaths within 28 days after the last dose and the corresponding reasons will be summarised. Also, all deaths overall will be summarised.

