## **6. Changes in the Conduct of the Study or Planned Analysis**

There were no changes in the analysis planned in the protocol of the study at the time of preparing this SAP.

Any deviations from the approved SAP will be described and justified in the CSR.

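### SAP 5.7.1 leaves out the protocol's summary of deaths within 28 days of the last dose, with reasons, and gives no cut-off for the overall death count it keeps

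*SAP*

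**What the plan says.** Protocol section 10.6.1.1 plans a fixed-window summary: "Deaths within 28 days after the last dose and the corresponding reasons will be summarised". It then adds a second one: "Also, all deaths overall will be summarised".

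SAP section 5.7.1 has a single sentence on deaths: "All deaths overall will be summarized and listed". It gives no window, no reasons and no cut-off date. SAP section 6 states: "There were no changes in the analysis planned in the protocol of the study at the time of preparing this SAP".

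Protocol section 9.3.5.8 says how deaths in the adverse event reporting period are captured. Those attributed solely to progression of the cancer "will be recorded on the EoT/EoS pages in the eCRF and not as an Adverse Event".

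On how long deaths are followed, Protocol section 8.1 gives the escalation cohorts one year: "Survival follow-up (e.g. per telephone) for 1 year is planned every three months after the End-of-study visit". For the confirmatory cohort and Part B the same section continues "and every six months thereafter for the" second year. Footnote 17 of Protocol Appendix 1, which covers the whole of Part A, gives one year only, and so does footnote 17 of SAP Appendix 3.

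**The concern.** SAP section 5.7 calls the safety analysis the primary analysis and has it summarised within cohort. In a first-in-human dose escalation, deaths on or shortly after treatment are a basic part of that picture. A count of deaths from any cause in a defined period around treatment has a particular use: its total does not depend on whether the investigator blamed the drug or the disease. That judgement can be difficult here. Protocol section 2.5.6 reports that the one serious event considered related so far was drug-induced liver injury in a patient whose cancer extensively involved the liver.

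If the SAP is followed as written, a patient who dies within four weeks of the last dose, with the death put down to progression, is in no fatal adverse event table. That patient is counted among all deaths, with nothing to show that the death was early. The omission would also go unreported: Protocol section 10 and SAP section 6 both measure deviations in the study report against the SAP, not against the protocol.

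**Working it through.** No sample size, power or error rate is involved and the documents give no figure to reproduce, so the main check is a comparison of texts.

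**Step 1. The two death plans side by side**

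| Item | Protocol v4.3, 10.6.1.1 | SAP v2.0, 5.7.1 |
|---|---|---|
| Deaths within 28 days of last dose | Summarised | Absent |
| Reasons for those deaths | Summarised | Absent |
| All deaths | Summarised | Summarised and listed |
| Data cut-off for all deaths | Not stated | Not stated |

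**Step 2. Could the SAP be following different protocol text?** SAP section 1 cites protocol v4.1 (3 August 2020), which was not available for this review. The SAP is dated 29 April 2022, about eleven months after protocol v4.3 (28 May 2021), which contains the 28-day sentence. The mismatch with the current protocol therefore stands, whatever v4.1 said.

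**Step 3. Do other planned outputs supply the missing count?**

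- Adverse event summaries by cohort include grade and outcome (SAP 5.7.1), and events are reported until four weeks after the last dose (Protocol 9.3.1). Deaths attributed solely to progression are excluded (Protocol 9.3.5.8).
- The DLT table is limited to cycle 1 and to events judged unrelated to progression (synopsis, DLT definition), so it rests on the same attribution.
- Disposition by cohort gives reasons for stopping treatment and study (SAP 5.2). Some of these deaths may appear there, but the reason categories are not specified and no time from last dose is attached.
- Kaplan-Meier overall survival is given for dose groups of at least 6 (SAP 5.6.2.5), while cohorts are planned at 3 to 6. It runs from first dose and carries no reasons.
- All data are listed (SAP 5.1), so the count can be rebuilt by hand.

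None of these is a pre-specified table of early deaths from any cause.

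**Step 4. What period does the overall count cover?** SAP 5.1 places the final analysis after every patient has stopped treatment and completed safety follow-up, and sends additional long-term survival data to a separate combined report. It does not say whether deaths found in survival follow-up before that date enter the table in 5.7.1. Cohorts enrol in sequence, so the follow-up accrued at any one date can differ between dose levels.

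**Step 5. Illustration of how far the two counts can diverge.** Assume constant hazard from the last dose with median survival M months, so that the share dead by time t is 1 − 2^(−t/M). With 30.4375 days per month, 28 days is 0.92 months, 28 days plus one year (393 days) is 12.91 months, and 28 days plus two years (758 days) is 24.90 months. M = 29.6 is the protocol's background figure for NOTCH1-mutant adenoid cystic carcinoma (section 2.2). M = 12 and M = 6 are assumptions to show the range.

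| M (months) | Dead by 28 days | By 28 days + 1 year | By 28 days + 2 years |
|---|---|---|---|
| 29.6 | 2.1% | 26.1% | 44.2% |
| 12 | 5.2% | 52.6% | 76.3% |
| 6 | 10.1% | 77.5% | 94.4% |

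The part of the one-year count that lies in the 28-day window is 2.1/26.1 = 8%, 5.2/52.6 = 10% and 10.1/77.5 = 13%. If survival follow-up enters the overall count, most of that count is late deaths, and it depends strongly on the length of follow-up.

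**The case against.** The best case for the SAP is that this is a small reporting gap with much of the information available elsewhere. Non-progression fatal events appear by cohort over the same four-week period, survival curves handle unequal follow-up by censoring, and dates are listed. The SAP also disclaims inferential comparison of dose groups. All of that is correct, and it limits the point. It does not supply the missing table.

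Several stronger readings are tempting and do not hold:

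- **Deaths cannot be compared by dose.** The outputs just named, and the listings, allow a good deal of comparison. What is lost is a pre-specified table.
- **The planned death window differs between cohorts.** Protocol section 8.1 suggests so for the confirmatory cohort, but footnote 17 in both schedules gives all of Part A one year. Among escalation dose levels the planned length is the same throughout; only accrued follow-up at the cut-off can differ.
- **The 28-day count is the only one with the same window in every cohort.** Counted from first dose it covers treatment duration plus 28 days, and treatment normally runs until progression or toxicity. It does not equalise exposure.
- **The summary was knowingly removed and the statement in SAP section 6 is false.** Without protocol v4.1 neither can be shown.

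The percentages above are also open to challenge. They assume that full survival follow-up enters the overall table, which SAP 5.1 does not say, and they apply a background survival figure from the last dose.

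**Conclusion.** The point stands as an undeclared omission relative to protocol v4.3. SAP 5.7.1 lacks the 28-day death summary with reasons, and the overall count it keeps has no stated cut-off. Because progression deaths are kept out of the adverse event tables, no pre-specified table by cohort shows early deaths from any cause.

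Its size is one table in the declared primary analysis. It should be corrected, but it does not undermine the dose-finding, and the count remains recoverable from listings. The conclusion rests on the texts alone. The 8% to 13% is illustrative and depends on constant hazard, the chosen medians and full survival follow-up entering the table. One qualification: Protocol 10.6.1.1 does not itself specify presentation by cohort. That follows from SAP 5.7, which has all safety assessments summarised within cohort.

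**What to change.** 1. In SAP 5.7.1, restore the number and percentage of deaths from any cause between first dose and 28 days after last dose, by cohort, with reason (progression, adverse event, other). Derive it from the end-of-treatment/end-of-study pages and the adverse event pages together. Show treatment duration alongside, since the window includes it.
2. For the overall death count, state the data cut-off and whether survival follow-up deaths are included, and give the follow-up for each cohort.
3. Reconcile the confirmatory cohort's survival follow-up in Protocol section 8.1 with footnote 17 of Protocol Appendix 1 and of SAP Appendix 3.
4. Update the protocol version cited in SAP section 1, and have section 6 declare any departure from v4.3 that remains.

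The cost is a few sentences in the SAP and one table from data already collected, plus a clarification of the follow-up schedule.
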